**Table 1 Schedule of Assessments and Study Activities**

Visit Window (days)	Prescreening and Screening Visits may be combined at site			Cycle 1		Cycle $\geq 2$				End of Treatment Visit	Safety Follow-up Call 	Survival Follow-up 
	Pre-Screening for DLBCL Subtyping 	Screening (prior to start of study treatment)										
		$\leq 30$ days prior to enrollment	$\leq 14$ days	$\leq 7$ days	Day 1 of Weeks 1-4	Day 3 of Week 1 only 	Day 1 of each cycle	Day 10 of each cycle 	Day 15 of each cycle	Day 24 of each cycle 	$\leq 14$ days after last dose	30 days after last dose
Study Visit #	Pre-Screen	Visit 1	Visit 2	Visits 3-6	Phone	Visits $\geq 7$	Phone	Visits	Phone	Visits	Phone	Phone
ICF for Pre-Screen of DLBCL subtyping 	X											
Signing ICF 	X											
Tumor biopsy (subjects without known DLBCL subtype and no archival tissue for subtyping) 	X											
Tumor biopsy (subjects with known DLBCL subtype but no archival tissue for subtyping) 		X										
Inclusion and exclusion criteria		X	X									
Demographics		X										
Disease risk assessment (Revised International Prognostic Index: R- IPI)		X										
Medical history 		X	X									

Height 		X									
Weight 		X	X	X		X		X		X	
Vital signs 			X	X		X				X	
ECOG score			X	X 		X 				X	
Physical examination 			X	X		X		X		X	
Echocardiogram or MUGA scan 		X									
12-lead ECG 		X								X	
Ophthalmic exam 		X				X					
Urinalysis 			X	X 		X 				X	
CBC with differential 			X	X 		X 				X	
TSH 			X	X 		X 				X	
Serum chemistry (Complete) 			X	X 		X 				X	
Serum chemistry (Limited) 				X			X				
Coagulation tests 			X							X	
Pregnancy test 			X			X				X	
HBV/HCV/HIV testing 			X			X					
Confirmation of PD and SD 		X									
PET-CT or enhanced CT scan for tumor assessment 		X				X					
Revised criteria for response assessment of lymphoma 						X					

Bone marrow aspirate and/or biopsy 		X										
5-HT3 antagonist dosing 				X								
ATG-010 dosing 				X		X	X					
Adverse events		X (adverse events beginning at after first dose of study drug, serious adverse events beginning at before first dose of study drug)										
Concomitant medication		X (beginning at ICF signing)										
Supportive care 		X		X		X		X				
Information on antineoplastic therapy after end of ATG-010 treatment 											X	

5-HT3 = 5-hydroxytryptamine ; ALT = alanine aminotransferase; aPTT = activated partial thromboplastin time; AST = aspartate aminotransferase, BUN = blood urea nitrogen; CBC = complete blood count; CR = complete response; CT = computed tomography; DLBCL = diffuse large B-cell lymphoma; ECG = electrocardiogram; ECOG = Eastern Cooperative Oncology Group; GCB = germinal center B-cell; HBV = hepatitis B virus; hCG = human chorionic gonadotropin; HCV = hepatitis C virus; HIV = human immunodeficiency virus; ICF = informed consent form; INR = international normalization ratio; LDH = lactate dehydrogenase; MRI = magnetic resonance imaging; MUGA = multiple gated acquisition; PET = positron emission tomography; PR = partial response; PT = prothrombin time; TSH = thyroid stimulating hormone; TT = thrombin time; WBC = white blood cell.

- 1 The patient must provide informed consent for pre-screening and master ICF within 30 days of enrollment and prior to the first screening procedure.
- 2 All subjects must submit either a fresh biopsy or archival tissue to the central DLBCL subtyping laboratory for determination (prior to enrollment) or confirmation (by end of Cycle 2) of their DLBCL pathological diagnosis and subtype. In subjects with a known DLBCL subtype but without sufficient archival tissue available for confirmatory subtyping, biopsy should be performed before the end of Cycle 1.
- 3 Medical History at Screening Visits 1 & 2 including baseline symptoms as well as a detailed history of prior cancer therapies and procedures for DLBCL with start and stop dates, best response and disease progression during or after therapy, as well as discontinuations due to intolerance or any other serious illness. An evaluation of the risk of tumor lysis syndrome based on a clinical evaluation of comorbidity will also be performed.
- 4 Height (will be only measured once at Screening Visits 1 or 2).
- 5 Body weight will be measured at each clinic visit up to and including Cycle 5; Cycle 6 onwards only during Day 1 visits.
- 6 The vital sign includes blood pressure, pulse, temperature, and respiration rate; will be measured after the patient has been in a supine or sitting position for 5 minutes, on Day 1 of each Cycle only.
- 7 On Day 1 of each Cycle only.
- 8 Full physical exam will be conducted on all subjects at screening and at the End of Treatment Visit; symptom-directed physical examination will be conducted during the study.
- 9 Echocardiogram or MUGA scan to be performed during Screening Visit 1 to assess baseline cardiac function and risk of cardiac dysfunction (including cardiomyopathy), particularly in subjects who have received prior anthracycline therapy.
- 10 An ECG will be done at Screening Visit 1, otherwise only if clinically indicated, and at End of Treatment Visit.
- 11 Ophthalmic exam will be conducted on the subjects with previous ocular or visual diseases or clinical indications at Screening; during the study, ophthalmological exam should be carried out if there are clinical indications, and an ophthalmologist should be consulted if necessary.

- 12 Urinalysis will be done at Screening Visit 2, Day 1 of each cycle, and End of Treatment Visit; and will include urine bilirubin, glucose, red blood cells, ketones, pH, protein, specific gravity, and urobilinogen. Microscopy will only be performed if clinically indicated.
- 13 The CBC with differential at Screening Visit 2, Day 1 of each cycle, and End of Treatment Visit, will include hemoglobin, hematocrit, mean corpuscular volume, mean corpuscular hemoglobin, mean corpuscular hemoglobin concentration, WBC count, WBC differential, RBC count, lymphocytes, monocytes, neutrophils, eosinophils, basophils, platelets. The WBC differential may be automated or manual as per institutional standards. Reticulocytes may be done only when clinically indicated.
- 14 The level of TSH will be measured at Screening Visit 2, Day 1 of each cycle, and End of Treatment Visit.
- 15 Complete serum chemistry at Screening Visit 2, Day 1 of each cycle, and End of Treatment Visit, will include sodium, potassium, chloride, bicarbonate, blood urea/BUN, creatinine, glucose, calcium, phosphate, magnesium, ALT, AST, alkaline phosphatase, total bilirubin, LDH, total protein, albumin, amylase, lipase, creatine kinase, and uric acid.
- 16 Limited chemistry for Cycle 1 (Weeks 2, 3 and 4) and Day 15 of Cycles  $\geq 2$  including sodium, potassium, chloride, bicarbonate, blood urea/BUN, creatinine, glucose, ALT, AST, alkaline phosphatase, total bilirubin, and LDH (otherwise other clinical indicated). If total bilirubin concentration increases to more than 1.5 times the upper limit of normal, total bilirubin will be divided into direct and indirect bilirubin.
- 17 Coagulation Tests to be measured at Screening Visit 2 and End of Treatment Visit including PT, INR, and aPTT. Coagulation may also be measured using TT (quick test) if measurement of PT/aPTT is not feasible. If there are coagulation related problems, the investigator may decide to retest at any time at his discretion.
- 18 Women of child bearing potential must have a negative serum hCG pregnancy test within 3 days prior to first study dose and at End of Treatment Visit. Women of child bearing potential will have urine pregnancy test on Day 1 of Cycle 2, then on Day 1 of even numbered cycles thereafter. A positive urine pregnancy test will be confirmed by a serum pregnancy test.
- 19 Screening for HBV and HCV at Screening Visit 2. HBV-DNA testing (only for HBcAb positive subjects) should be done each cycle (approximately monthly). At Screening Visit 2, HIV testing is required if the patient is known to have prior HIV infection.
- 20 Confirmed evidence of DLBCL disease progression (PD) or failure (SD) to the last treatment regimen is required for study entry, and subjects must have measurable disease at screening per the Lugano criteria for response assessment of lymphoma (*Cheson, 2014*).
- 21 Disease assessment (tumor measurement) will be made by PET-CT and Contrast-enhanced CT (Tumor measurement) at screening (within the first 14 days of Cycle 1 Day 1), enhanced CT should include the neck, chest, abdomen, pelvic cavity (including the inguinal/femoral region), if clinically indicated, as well as other anatomical sites. If CT is contraindicated, MRI scan will be performed. PET-CT and contrast-enhanced CT scans will be performed on Cycle 3 Day 1 ( $\pm 1$  week) and then every 8 $\pm 1$  weeks (ie, Day 1 of odd numbered cycles) until disease progression is confirmed by the central radiological review. The PET-CT is allowed at alternating assessment time points (ie, every 16 weeks, or every other scan) if PET-CT cannot be performed for every assessment. If CT scan suggests the possibility of obtaining CR, PET-CT should be performed for confirmation. Results of PET-CT and contrast-enhanced CT scans performed beyond a predetermined time point should be recorded on the eCRF and images of all disease assessment scans performed during the study period will be provided to the central radiological review.
- 22 Disease status will be assessed by the Lugano criteria for response assessment of lymphoma (*Cheson, 2014; Appendix 1*) on Cycle 3 Day 1 ( $\pm 1$  week) and then every 8 weeks  $\pm 1$  week (ie, Day 1 of odd numbered cycles) until disease progression is confirmed by the central radiological review.
- 23 Bone marrow aspirates and/or biopsies will be taken within 1 month prior to first dose (baseline) to assess DLBCL involvement in bone marrow. The bone marrow biopsy will be repeated whenever clinically indicated to confirm CR in only those subjects who had DLBCL known bone marrow involvement prior to dosing.
- 24 To minimize nausea, all subjects should receive 5-HT3 antagonists (8 mg or equivalent) unless contraindicated, starting on Cycle 1 Day 1 before the first dose of ATG-010 and continued 2 to 3 times daily thereafter, as needed. Olanzapine is also recommended for the first 8 weeks, after which the dosage can be gradually reduced according to the situation of patient.
- 25 ATG-010 dosing will occur on Days 1 and 3 of Weeks 1-4 of each 4-week cycle. For doses on non-clinic days, the patient will be provided doses to take home.
- 26 Phone call to evaluate supportive care medications and adverse events, and to adjust supportive care as appropriate. In Cycle 1, the telephone contact with the patient must take place on Day 3 (+ 1 day) following the Cycle 1 Day 1 of ATG-010 dosing. For Cycles  $\geq 2$ , this phone call will be made on Day 10 (+ 1 day) and 24 (+ 1 day), corresponding to Day 3 (+ 1 day) of every week in which a clinic visit does not occur.
- 27 By phone (or a visit, if possible), assess patient status, follow-up on any adverse events that were not resolved at the End of Treatment Visit, and information on any antineoplastic therapies utilized since discontinuation of study treatment.

28 After treatment discontinuation, a call will be made to the patient (or the patient's family) every 3 months ( $\pm$  14 days) from the date their last dose until the End of Study to determine the patient's survival status and information on any antineoplastic therapies utilized since discontinuation of study treatment.

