- b. HCV antibody positive. But subjects with positive HCV antibodies can be enrolled if HCV-RNA cannot be detected.

13. Known human immunodeficiency virus (HIV) infection.

14. Subjects unable to swallow tablets, subjects with malabsorption syndrome, or any other gastrointestinal disease or gastrointestinal dysfunction that could interfere with absorption of study treatment of ATG-010.

15. Any of the following laboratory abnormalities (without corrective treatment)

- a. Absolute neutrophil count <1000 cells/mm^3 or platelet count <75,000/mm^3 during screening and on C1D1. Platelet infusions within 1 week prior to the first study treatment and/or use of granulocyte-stimulating factors and platelet growth factors 2 weeks prior to the first study treatment
- b. A circulating lymphocyte count of >50,000/ $\mu$ L
- c. Hepatic dysfunction: bilirubin >2.0 times the upper limit of normal (ULN) (except subjects with Gilbert's syndrome: total bilirubin of > 3×ULN) and alanine aminotransferase (ALT) and aspartate aminotransferase (AST) >2.5 ×ULN. In subjects with known liver involvement of their DLBCL, AST and ALT >5 ×ULN
- d. Severe renal dysfunction: estimated creatinine clearance of <30 mL/min, measured in 24-hour urine or calculated using the formula of Cockcroft and Gault (can refer to Appendix 5)
- e. Hematopoietic dysfunction: hemoglobin <10.0 g/dL within 14 days of and including C1D1 and/or subjects receiving red blood cell transfusion within 14 days of and including C1D1.

16. Subjects with a body surface area <1.4 m^2 (can refer to Appendix 6).

17. Psychiatric illness or substance use that would prevent the patient from giving informed consent or being compliant with the study procedures.

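### On treatment, the blood count is scheduled only on Day 1 of each 4-week cycle, so the first routine post-dose count is Day 29, although blood is already drawn in between

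*Combined protocol and SAP*

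**What the plan says.** All references are to the combined protocol and SAP, Table 1 and its footnotes, unless another section is named.

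- **Blood count.** Footnote 13 places it as follows: "The CBC with differential at Screening Visit 2, Day 1 of each cycle, and End of Treatment Visit". Both on-treatment marks in the CBC row carry footnote 7, which restricts them to a test "on Day 1 of each Cycle only". The Cycle 1 column covers the first day of Weeks 1 to 4, but this restriction leaves a single count in that cycle.
- **Draws between counts.** Footnote 16 schedules "Limited chemistry for Cycle 1 (Weeks 2, 3 and 4) and Day 15 of Cycles" ≥2. Its analytes are electrolytes, urea, creatinine, glucose, liver tests and LDH, with no count. A parenthesis in the same footnote leaves room for other clinically indicated tests.
- **Dosing.** Footnote 25: "ATG-010 dosing will occur on Days 1 and 3 of Weeks 1-4 of each 4-week cycle". The section on test product and dose gives 8 doses of 60 mg per cycle, and 60 mg once weekly on maintenance.
- **Other checks at the in-between visits.** Adverse events and concomitant medication are collected throughout. Under footnote 8, "symptom-directed physical examination will be conducted during the study". Footnote 5 has weight measured at every clinic visit through Cycle 5 and only on Day 1 visits from Cycle 6. Vital signs, temperature included, are taken "in a supine or sitting position for 5 minutes, on Day 1 of each Cycle only" (footnote 6). Footnote 26 adds phone calls about supportive care and adverse events.

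**The concern.** Safety and tolerability is a secondary objective, and the Safety Assessment section includes haematology among the analysed endpoints. Exclusion criterion 15a admits subjects with neutrophils as low as 1000/mm³ and platelets as low as 75,000/mm³, checked at screening and again on Cycle 1 Day 1. Routine counting then stops for 28 days, while liver and kidney tests are repeated weekly through Cycle 1.

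The dose section makes the modification depend on toxicity grade, and an asymptomatic low count cannot be graded unless a count is taken. Two things are at stake. One is subject safety: a silent early fall could go unseen for up to 28 days of dosing unless someone orders an unscheduled count. The other is the completeness of the haematology data, in a study whose size is justified partly by the need for sufficient safety data in Chinese subjects. The contrast with the chemistry schedule is what draws attention, because the needle is already in the arm and the text provided gives no reason for leaving the count out.

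**Working it through.** This is a count of the calendar; no power or sample-size formula applies.

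**Inputs.** Dosing days (footnote 25), dose and maintenance dose (test product section), count days (footnotes 7 and 13), limited-chemistry days (footnote 16), about 60 subjects (Study Design).

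**Step 1: reproduce the plan's dose count.** Dosing on Days 1 and 3 of each week falls on Days 1, 3, 8, 10, 15, 17, 22 and 24. That is 8 doses per cycle, as the plan states.

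**Step 2: current schedule.** Counts fall on Days 1, 29, 57, 85 and so on. The planned doses given before each are 0, 8, 16 and 24. The Day 1 count is an eligibility count taken before dosing, so the first routine post-dose count is Day 29, after 8 × 60 = 480 mg. The gap is 29 − 1 = 28 days.

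**Step 3: blood drawn without a count.** Days 8, 15 and 22 of Cycle 1, and Day 15 of every later cycle. With Day 1 included, Cycle 1 has 4 chemistry draws against 1 count, and each later cycle has 2 against 1.

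**Step 4: add a count to those draws.** Counts would fall on Days 1, 8, 15, 22, 29, 43, 57, 71, 85 and so on.

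| | Current | With added counts |
|---|---|---|
| First post-dose count | Day 29 | Day 8 |
| Cycle 1: counts | 1 | 4 |
| Cycle 1: longest gap | 28 days | 8 − 1 = 7 days |
| Cycle 1: doses between counts | 8 (480 mg) | 2 (120 mg) |
| Later cycles: counts | 1 | 2 |
| Later cycles: longest gap | 28 days | 15 − 1 = 14 days |
| Later cycles, twice weekly: doses between counts | 8 (480 mg) | 4 (240 mg) |
| Later cycles, once-weekly maintenance: doses between counts | 4 (240 mg) | 2 (120 mg) |

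**Step 5: subjects who stop in Cycle 1.** They rely on the End of Treatment count, due within 14 days of the last dose. At the outer limit, a last dose on Day 24 gives Day 24 + 14 = Day 38. This is an extreme case, dosing has ended by then, and the conclusion does not rest on it.

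**Step 6: volume of extra tests.** Cycle 1 only: 3 per subject, so at most 3 × 60 = 180. With Day 15 of later cycles as well, a subject completing k cycles has 3 + (k − 1) extra counts: 5 for k = 3 and 8 for k = 6.

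**The case against.** The strongest reply is that no deficiency has been shown. The figures above describe a calendar; the documents contain no rate, timing or duration of cytopenia. The one remark on normal cells, in the Study Rationale, says that the drug affects them little, although it rests on preclinical work. A low that persists under continuous dosing would appear at the next Day 1 count. Subjects also enter on unsupported counts: criterion 15 bars recent platelet or red-cell transfusion and recent growth factors, and requires haemoglobin of at least 10.0 g/dL. This stands, and it is why no number of missed events is offered.

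Second, the text provided is a synopsis with Table 1. It refers to grade-driven dose modification without giving the full rules, and these may call for repeat counts. That also stands, and it limits the point to the routine schedule. Rules that a low count triggers would still need a first count to trigger them.

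Third, the in-between visits are not empty. Adverse events are collected, the subject is examined for symptoms, and footnote 16 leaves room for further tests. A reader might infer that counts between Day 1 visits are prohibited, or that subjects go unobserved for four weeks. The documents support neither. What remains is narrower: these checks respond to symptoms or clinical suspicion and do not reliably find a silent low.

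Fourth, extra counts are not neutral in a bridging study. Lows found at added draws can be recorded as adverse events and can lead to dose reductions or delays. Changed exposure could affect the response rate, which is judged by whether its point estimate falls within the SADAL interval (20.7% to 37.0%), and also the 70% compliance criterion for the per-protocol population. The SADAL count schedule is not shown, so the change could create a difference as easily as remove one. This is a genuine cost and should be stated.

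**Conclusion.** The point holds as a worthwhile, inexpensive improvement to the routine schedule. The table row and the footnotes agree: a continuing subject has one scheduled count per 28 days, and the first after dosing starts comes on Day 29, following 8 planned doses. The gain from a change is largest in Cycle 1 (28 to 7 days between counts, 8 to 2 doses before the first post-dose count). It is smaller in later cycles (28 to 14 days), and smaller again in doses on once-weekly maintenance.

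The day counts assume no dose delay, no use of visit windows and sampling before that day's dose. The limited-chemistry mark for later cycles may be shifted by a column in the extracted table; footnote 16 settles it as Day 15.

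A reader might go further and infer that the schedule is an error, or that cytopenias will be missed at some material rate. The documents do not support this: they give no frequency for such events, and the full dose-modification rules cannot be checked here.

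**What to change.** 1. Amend footnotes 7, 13 and 16 to add a CBC with differential to the limited-chemistry draws in Cycle 1 Weeks 2, 3 and 4. This is the part to adopt if only one is adopted.
2. Optionally, add it on Day 15 of Cycles ≥2 as well.
3. Include the added values in the haematology summaries, and also summarise Day 1 laboratory values alone.
4. In any comparison with SADAL, state that count frequency may differ and may influence adverse-event counts, dose modifications and exposure.

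No change to the dose or to the modification rules is proposed.

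The cost is one more tube at an existing draw, with no new visit or venepuncture. Recorded cytopenia rates may rise because more counts are taken. The Day-1-only summary deals with this only in part, since dose changes prompted by an added count also alter later Day 1 values and recorded adverse events.

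### Uric acid, phosphate and calcium have no scheduled value between Cycle 1 Day 1 and Cycle 2 Day 1, although tumour lysis risk is evaluated at screening

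*Combined protocol and SAP*

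**What the plan says.** Four footnotes to Table 1 (Schedule of Assessments and Study Activities) bear on this point.

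- **Footnote 3 (medical history, Screening Visits 1 and 2):** "An evaluation of the risk of tumor lysis syndrome based on a clinical evaluation of comorbidity will also be performed".
- **Footnote 15 (complete chemistry):** timing and opening of the list are "Complete serum chemistry at Screening Visit 2, Day 1 of each cycle, and End of Treatment Visit, will include sodium, potassium". The list goes on to include "creatinine, glucose, calcium, phosphate, magnesium, ALT, AST" and ends with "total protein, albumin, amylase, lipase, creatine kinase, and uric acid". Calcium, phosphate and uric acid are therefore all in this panel.
- **Footnote 7**, attached to the complete-chemistry row in the Cycle 1 and later-cycle columns, restricts it to a draw "on Day 1 of each Cycle only".
- **Footnote 16 (limited chemistry):** the timing begins "Limited chemistry for Cycle 1 (Weeks 2, 3 and 4) and Day 15 of Cycles" 2 and later, and the content is "including sodium, potassium, chloride, bicarbonate, blood urea/BUN, creatinine, glucose, ALT, AST, alkaline phosphatase, total bilirubin, and LDH". A parenthesis follows. Its wording is garbled, but it appears to allow other tests when clinically indicated.

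The Safety Assessment section plans to analyse blood chemistry in the safety population, and safety and tolerability is a secondary endpoint. The supplied text does not define laboratory tumour lysis and does not name it as an outcome.

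**The concern.** The plan names tumour lysis as a risk to be weighed before treatment. Three analytes commonly used to describe it biochemically are then absent from the routine panel throughout the first exposure period. That these analytes are relevant is general clinical knowledge; the documents do not say so.

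What is at stake is how complete the early safety data are. A change in uric acid, phosphate or calcium that appears in Cycle 1 and resolves by Day 29 leaves no scheduled record unless someone orders an extra test. Extra tests depend on clinical recognition, so asymptomatic changes are the ones most likely to be missing. The study has one arm, so there is no concurrent comparison that would reveal under-recording. The sample-size section also gives sufficient safety data in Chinese subjects as one of the aims of enrolling 60.

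**Working it through.** **Step 1. Reproduce the dose count.** Footnote 25 places dosing on Days 1 and 3 of Weeks 1 to 4. With day = 7 × (week − 1) + 1 or + 3, the dosing days are 1, 3, 8, 10, 15, 17, 22 and 24. That is 2 × 4 = 8 doses, which matches the 8 per cycle stated under Test Product, Dose and Mode of Administration.

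**Step 2. Compare the panels.** Footnote 15 lists 21 analytes and footnote 16 lists 12, all of which are also in footnote 15. The 21 − 12 = 9 omitted are uric acid, phosphate, calcium, magnesium, creatine kinase, lipase, amylase, albumin and total protein. Potassium, creatinine, BUN and LDH are in both panels.

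**Step 3. Lay the draws against the doses.** This uses nominal visit days, no held doses, and draws taken before that day's dose.

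| Visit | Day | Planned doses already given | Panel | Uric acid, phosphate, calcium |
|---|---|---|---|---|
| Cycle 1 Day 1 | 1 | 0 | complete | yes |
| Week 2 | 8 | 2 | limited | no |
| Week 3 | 15 | 4 | limited | no |
| Week 4 | 22 | 6 | limited | no |
| Cycle 2 Day 1 | 29 | 8 | complete | yes |

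**Step 4. Size of the gap.** The interval between scheduled values of the three analytes is 29 − 1 = 28 days. It contains 8 planned doses and three chemistry draws that do not report them. Baseline is covered twice, at Screening Visit 2 and Cycle 1 Day 1, so only post-dose values are missing.

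**Step 5. Effect of adding the three analytes to the limited panel in Cycle 1.** Scheduled values would fall on Days 1, 8, 15, 22 and 29, and the longest interval would drop from 28 to 7 days. Days 2 to 7, which contain the Day 3 dose, would still have none.

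**The case against.** The strongest case against is that the plan has no error here. Footnote 3 asks for a screening judgement based on comorbidity and promises no laboratory follow-up. A sponsor may reasonably use that judgement to decide who needs further tests, and footnote 16 appears to leave room for them. Other surveillance is also scheduled in Cycle 1: weekly potassium, creatinine, BUN and LDH, a clinic visit each week, and a Day 3 telephone call covering adverse events. A subject who stops in Cycle 1 has the complete panel at End of Treatment, within 14 days of the last dose and possibly before Day 29. No laboratory tumour lysis outcome is planned, and no efficacy analysis is touched. The supplied text is a synopsis with its schedule table, so a relevant section in a fuller protocol cannot be excluded.

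Most of this stands, and it rules out three stronger readings that a reader might infer:

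- **That laboratory tumour lysis is unmonitored until Cycle 2.** Potassium and the renal measures are drawn weekly; only three analytes lack a scheduled value.
- **That footnotes 3 and 16 contradict each other.** One concerns a risk evaluation at screening, the other the content of a later panel. Both can be followed as written.
- **That some number of the 60 subjects would have unrecorded events.** The documents give no incidence or timing of tumour lysis for this study or for SADAL, so no count can be derived.

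The objection does not remove the recording gap. Tests ordered on clinical indication do not give a uniform data set, and the weekly samples that could supply one are already taken.

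**Conclusion.** The point holds as a limited gap in data collection. For subjects who remain on treatment, uric acid, phosphate and calcium have no scheduled value for 28 days, across all 8 planned Cycle 1 doses, while three chemistry samples are drawn without them. The consequence is less complete early data for the blood-chemistry safety analysis. The gap does not extend to all tumour lysis surveillance, and it does not affect the primary endpoint.

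The 28-day figure assumes nominal visit days. The 8-dose figure also assumes no held or delayed doses. The conclusion rests on the schedule table as supplied and does not depend on any assumed event rate. It is a low-cost improvement to the plan and does not correct an inconsistency.

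**What to change.** In Table 1, footnote 16, add uric acid, phosphate and calcium to the limited chemistry for Cycle 1 Weeks 2, 3 and 4, run on the samples already drawn. State that the purpose is data collection for the planned blood-chemistry safety analysis. No dose, prophylaxis, stopping or other management rule changes.

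The cost is three routine assays on up to three existing samples, so at most 3 × 3 = 9 assays per subject and 9 × 60 = 540 across the planned 60 subjects. There is no extra visit or blood draw. Because the first added value is on Day 8, after 2 planned doses, the change narrows the gap without closing it.
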